1	Talquetamab	Medical claim with an NDC, HCPCS, generic name or CPT code in the inpatient, non-IP, or pharmacy setting for talquetamab (dichotomous)	MM diagnosis to 1 day prior to index date
			Index date to the end of follow-up
1	PIs	Medical claim with an NDC, HCPCS, generic name or CPT code in the inpatient, non-IP, or pharmacy setting for bortezomib, carfilzomib, or ixazomib	MM diagnosis to 1 day prior to index date
		(dichotomous)	Index date to the end of follow-up
1	IMiDs	Medical claim with an NDC code or generic name in the non-IP or pharmacy setting for lenalidomide, thalidomide, or pomalidomide (dichotomous)	MM diagnosis to 1 day prior to index date
			Index date to the end of follow-up
1	Steroids	Medical claim with an NDC, HCPCS, generic name or CPT code in the inpatient, non-IP, or pharmacy setting for dexamethasone, methylprednisolone, prednisone, or prednisolone (dichotomous)	MM diagnosis to 1 day prior to index date
		prediffication, or prediffication (dieffotolificas)	Index date to the end of follow-up

Objective	Variable	Definition	Assessment Period(s)
1	mAbs	Medical claim with an NDC, HCPCS, generic name or CPT code in the inpatient, non-IP, or pharmacy setting for daratumumab, isatuximab, or elotuzumab (dichotomous)	MM diagnosis to 1 day prior to index date
			Index date to the end of follow-up
1	Chemotherapies	Medical claim with an NDC, HCPCS, generic name or CPT code in the inpatient, non-IP, or pharmacy setting for doxorubicin hydrochloride, melphalan, bendamustine, cyclophosphamide, etoposide, or	MM diagnosis to 1 day prior to index date
		cisplatin (dichotomous)	Index date to the end of follow-up
1	Small molecule inhibitors	Medical claim with an NDC, HCPCS, generic name or CPT code in the inpatient, non-IP, or pharmacy setting for venetoclax (dichotomous)	MM diagnosis to 1 day before index date
		setting for venerociax (dichotomous)	Index date to the end of follow-up
1	Nuclear export inhibitors	Medical claim with an NDC, HCPCS, generic name or CPT code in the inpatient, non-IP, or pharmacy setting for selinexor (dichotomous)	MM diagnosis to 1 day before index date
		coming for community (controlled as)	Index date to the end of follow-up
1	Antivirals	Medical claim with an NDC, HCPCS, generic name or CPT code in the inpatient, non-IP, or pharmacy setting for antiviral medications (dichotomous)	14 days prior to index date to 1 day prior to index date

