1	Rheumatic disease	Medical claim with an ICD-10 code in the inpatient or non-IP setting for rheumatic disease (dichotomous)	180 days prior to index date to index
1	Peptic ulcer disease	Medical claim with an ICD-10 code in the inpatient or non-IP setting for peptic ulcer disease (dichotomous)	180 days prior to index date to index
1	Liver disease	Medical claim with an ICD-10 code in the inpatient or non-IP setting for liver disease (dichotomous)	180 days prior to index date to index
1	Diabetes	Medical claim with an ICD-10 code in the inpatient or non-IP setting for diabetes (dichotomous)	180 days prior to index date to index
1	Renal disease	Medical claim with an ICD-10 code in the inpatient or non-IP setting for renal disease (dichotomous)	180 days prior to index date to index date
1	Hemiplegia or paraplegia	Medical claim with an ICD-10 code in the inpatient or non-IP setting for hemiplegia or paraplegia (dichotomous)	180 days prior to index date
1	Human immunodeficienc y virus	Medical claim with an ICD-10 code in the inpatient or non-IP setting for human immunodeficiency virus (dichotomous)	180 days prior to index date to index date

Objective	Variable	Definition	Assessment Period(s)
1	Metastatic solid tumor	Medical claim with an ICD-10 code in the inpatient or non-IP setting for metastatic solid tumor (dichotomous)	180 days prior to index date to index date

Table 3 includes definitions and assessment periods for all study variables being used as outcomes. The full code list can be found in ANNEX 2. ADDITIONAL INFORMATION. If applicable, the frequency and percentage of patients with missing data for each variable will be described.

Table 3. Key Variables of Interest

Objective	Variable	Definition	Assessment Period(s)
Treatment ex	posure		
2	Use of supportive MM medications	Medical or pharmacy claim with evidence of an NDC, HCPCS, generic name or CPT code for the following medications (dichotomous):	Index date to the end of follow-up Index date Step-Up Dosing Period Maintenance Periods
2	Reported vial size	Reported vial size in the following categories (categorical): • Unknown vial – inpatient dose • 44mg/1.1mL • 76mg/1.9mL • Missing dose/unknown dose For the cohort of teclistamab patients the reported vial size (categorical): • Unknown vial – inpatient dose • 30mg/3mL • 153mg/7mL • Missing dose/unknown dose	Index date to the end of follow-up Index date Step-Up Dosing Period Maintenance Periods

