ANNEX 2. ADDITIONAL INFORMATION

			Codes
Variable	Role	Data Source(s)	
Elranatamab	Inclusion criteria	Claims data	HCPCS: C9165, J1323 NDC: 00069449401, 00069449402, 00069252201, 00069252202 ICD-10 Procedure code: XW013L9 Generic name: Elranatamab
Teclistamab	Inclusion criteria	Claims data	HCPCS: J9380, C9148 NDC: 57894044901, 57894045001 ICD-10 Procedure code: XW013487Generic name: Teclistamab
Multiple Myeloma	Inclusion criteria, Outcome - HCRU	Claims data	C90.0x
Age	Inclusion criteria, Baseline characteristic - Demographic	Claims data	N/A
Sex	Baseline characteristic - Demographic	Claims data	N/A

Dagg/Etlan! -: t	Baseline	Claims	N/A
Race/Ethnicity	characteristic - Demographic	data data	N/A
US Census Region	Baseline characteristic - Demographic	Claims data	N/A
State	Baseline characteristic - Demographic	Claims data	- N/A
BCMA-directed therapy	Baseline characteristic - Treatments, Outcome - HCRU	Claims data	CPT: 0537T, 0538T, 0539T, 0540T HCPCS: C9081, C9098, Q2055, Q2056, J9037, C9069 NDC: 57894011101, 57894011102, 59572051501, 59572051502, 59572051503, 00173089601 Generic names: Idecabtagene Vicleucel, Ciltacabtagene Autoleucel, Belantamab ICD10PCS: XW033K7, XW043K7, XW043A7, XW043A7, XW033A7
CAR-T	Baseline characteristic - Treatments, Outcome - HCRU	Claims data	CPT: 0537T, 0538T, 0539T, 0540T HCPCS: C9081, C9098, Q2055, Q2056 NDC: 57894011101, 57894011102, 59572051501, 59572051502, 59572051503 Revenue codes: 0871, 0872, 0873, 0874, 0891 ICD10PCS: XW033C7 XW033G7 XW033J7 XW033K7 XW043C7 XW043G7 XW043K7 Generic names: Idecabtagene Vicleucel, Ciltacabtagene Autoleucel
Hematopoietic stem cell transplantation	Baseline characteristic - Treatments	Claims data	CPT: 38240, 38241, 38242, 38243 HCPCS: A52879, S2150 ICD-10 Diagnosis: T86.0, T86.00, T86.01, T86.02, T86.03, T86.09, T86.5, Z48.290, Z94.81, Z94.84 ICD-10 Procedure: 30240Y0, 30243Y0, 30250Y0, 30253Y0, 30260Y0, 30263Y0, 30230Y1, 30233Y1, 30240Y1, 30243Y1, 30230Y2, 30233Y2, 30240Y2, 30243Y2, 30230Y3, 30233Y3, 30240Y3, 30243Y3, 30230Y4, 30233Y4, 30240Y4, 30243Y4, 30253Y1, 30260Y1, 30263Y1, 30233X0,

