Use of premedication	Outcome - Dosing and Administration Patterns	Claims data	HCPCS: J1094, J1096, J8540, J1100, J0131, J7637, J7638, J7312, J1200, Q0163 Generic names (and associated NDCs): Acetaminophen, Dexamethasone, Diphenhydramine
Inpatient	Baseline characteristic, Outcome - HCRU	Claims data	Any event in the inpatient table or an event in the non-inpatient table where acute_subacute is "acute inpatient" or where utilization type is "professional services", and service subcategory contains the term "hospital/IP encounter"
Outpatient	Baseline characteristic, Outcome - HCRU	Claims data	Any event in the non-inpatient table where utilization type is outpatient and service subcategory is not "emergency dept encounter"

Emergency department	Baseline characteristic, Outcome - HCRU	Claims data	Any event in the non-inpatient table where utilization type is "outpatient" and service subcategory is "emergency dept encounter"
Cytokine release syndrome (CRS)	Safety events	Claims data	ICD-10 Diagnosis: D89.83x
Immune effector cell- associated neurotoxicity Syndrome (ICANS)	Adverse events	Claims data	ICD-10 Diagnosis: G92.0x
Anemia	Adverse events	Claims data	ICD-10 Diagnosis: D46.0, D46.1, D46.20, D46.21, D46.22, D46.4, D46.9, D46.A, D46.B, D46.C, D46.Z, D47.4, D50.0, D50.1, D50.8, D50.9, D51.0, D51.1, D51.2, D51.3, D51.8, D51.9, D52.0, D52.1, D52.8, D52.9, D53.0, D53.1, D53.2, D53.8, D53.9, D55.0, D55.1, D55.2, D55.21, D55.29, D55.3, D55.8, D55.9, D59.0, D59.1, D59.10, D59.11, D59.12, D59.13, D59.19, D59.2, D59.3, D59.30, D59.31, D59.39, D59.4, D59.5, D59.6, D59.8, D59.9, D60.0, D60.1, D60.8, D60.9, D61.01, D61.09, D61.1, D61.2, D61.3, D61.810, D61.811, D61.818, D61.82, D61.89, D61.9, D63.0, D63.1, D63.8, D64.9, D75.81
Lymphopenia	Adverse events	Claims data	ICD-10 Diagnosis: D72.810
Hypogammaglobulinemia	Adverse events	Claims data	ICD-10 Diagnosis: D80.1, D80.3, D80.9
Hypophosphataemia	Adverse events	Claims data	ICD-10 Diagnosis: E83.39
Hypokalaemia	Adverse events	Claims data	ICD-10 Diagnosis: E87.6
Arthralgia	Adverse events	Claims data	ICD-10 Diagnosis: M25.5x
Pyrexia	Adverse events	Claims data	ICD-10 Diagnosis: R50.x
Hypotension	Adverse events	Claims data	ICD-10 Diagnosis: I95.0, I95.81, I95.89, I95.9, I95.2
Fatigue	Adverse events	Claims data	ICD-10 Diagnosis: R53.x, G93.3x

Nausea or vomiting	Adverse events	Claims data	ICD-10 Diagnosis: R11.x
Diarrhea	Adverse events	Claims data	ICD-10 Diagnosis: R19.7, K59.1

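### Supportive-medication use (Table 3) has no level for unobservable inpatient doses, so use is likely understated at the index date and, to a lesser degree, in step-up

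*Protocol*

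**What the plan says.** Section 8 places supportive MM medication usage under primary Objective 2. Table 3 in section 9.3 defines it as a dichotomous variable requiring a "Medical or pharmacy claim with evidence of an NDC, HCPCS, generic name or CPT code for the following medications". It is reported over all follow-up and separately for "Index date Step-Up Dosing Period Maintenance Periods". Section 9.7.1 summarises such variables as number and percentage of patients and does not restrict them by care setting.

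Three other entries bear on this:

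- The next row of Table 3, reported vial size, covers the same windows. It has a level "Unknown vial – inpatient dose", distinct from its level for a missing or unknown dose.
- Annex 2 lets the index drug be found by procedure code (for elranatamab, "ICD-10 Procedure code: XW013L9"; teclistamab also has one). The premedication row lists only "HCPCS: J1094, J1096, J8540, J1100, J0131, J7637, J7638, J7312, J1200, Q0163" and "Generic names (and associated NDCs): Acetaminophen, Dexamethasone, Diphenhydramine".
- Table 2 collects the care setting of the index-drug administration (inpatient, non-inpatient, pharmacy) at the index, second and third treatment dates and overall. It is not linked to the supportive-medication row.

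The limitations in 9.9 mention drug use not directly reimbursed by Medicare, with over-the-counter purchase as the example. Drugs given during an inpatient stay are not named.

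**The concern.** A yes/no built on the presence of a claim is never missing: no claim means no. That is sound only where a claim would be expected if the drug had been given. For inpatient doses the protocol gives reason to doubt this. It treats inpatient product detail as structurally unknown even for the index drug, and its premedication code list has no counterpart to the procedure code by which an inpatient index-drug dose can be found. A patient can thus enter the cohort on an inpatient dose and be recorded as not premedicated because the record cannot show it.

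The published percentage for a primary-objective item would then mix actual use with the share of doses given in hospital, and nothing in the table would warn the reader. The two cohorts are reported separately. If their inpatient shares differ, their premedication figures would differ for that reason alone.

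**Working it through.** The protocol states no expected proportion for this variable, so there is no figure to reproduce.

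**Inputs**

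- True use *u*, inpatient share of index-date doses *s*, and probability *k* that an inpatient premedication appears as a drug-coded claim. None is in the protocol; all are assumptions.
- *u* is taken as equal in both settings, and non-inpatient use as fully captured.
- 133 patients with an elranatamab claim as of August 2024 (section 9.5). This is a count of claimants, not the final eligible cohort.

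**Index date**

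Observed use = *u* × [1 − *s*(1 − *k*)]. With *u* = 90%:

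| *s* | *k* = 0 | *k* = 50% |
|---|---|---|
| 30% | 0.9 × 0.70 = 63% | 0.9 × 0.85 = 76.5% |
| 50% | 0.9 × 0.50 = 45% | 0.9 × 0.75 = 67.5% |
| 70% | 0.9 × 0.30 = 27% | 0.9 × 0.65 = 58.5% |

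The direction is downward whenever *s* > 0 and *k* < 1. The shortfall is *u* × *s* × (1 − *k*), so half capture halves it.

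The planned 95% limits would not reveal the problem. For 45% with n = 133, the Wilson centre is (0.45 + 3.8416/266)/(1 + 3.8416/133) = 0.451. The half-width is 1.96 × √(0.45 × 0.55/133 + 3.8416/(4 × 133²))/1.0289 = 0.083. The interval is 36.8% to 53.5%, far from the assumed 90%.

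**Step-up**

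The variable is yes if any qualifying claim falls in the window. Table 4 expects three elranatamab administrations from index to day 8. Let *m* be the share of inpatient starters who also have a captured non-inpatient dose in the window; they are then observed like everyone else. With *k* = 0, observed use = *u* × [1 − *s*(1 − *m*)]. For *u* = 90% and *s* = 50%:

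- *m* = 0: 0.9 × 0.50 = 45%
- *m* = 30%: 0.9 × 0.65 = 58.5%
- *m* = 60%: 0.9 × 0.80 = 72%
- *m* = 100%: 0.9 × 1.00 = 90%

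The step-up shortfall comes from patients with no captured claim in the window. It does not follow from inpatient starts alone.

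**The case against.** The strongest objection is that the protocol nowhere says inpatient claims lack drug codes. The unknown-vial level concerns the vial size of the index drug, not dexamethasone, acetaminophen or diphenhydramine. Table 2 points the other way: its steroid row is a "Medical claim with an NDC, HCPCS, generic name or CPT code in the inpatient, non-IP, or pharmacy setting for dexamethasone", and the antiviral, antibiotic and antifungal rows are worded alike. The Annex 2 steroid row also has no procedure code, so the absence of one does not prove invisibility. Annex 2 further counts some events from the non-inpatient table as inpatient. This stands to the extent that zero capture (*k* = 0) is an assumption and not a fact in the document. It does not show good capture, because the setting phrase looks generic. The venetoclax and selinexor rows of Table 2 promise HCPCS and CPT codes while Annex 2 lists only NDCs and names, and the adverse-event rows of Table 3 place diagnosis codes in the pharmacy setting.

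A reader might infer that use is understated in strict proportion to inpatient starts. That holds on the index date for a constant *k*, but not over the multi-dose step-up window.

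It can also be said that existing provisions suffice: missing categories in 9.7.1, care setting in Table 2, and detail left to the SAP. These help only in part. An unseen claim is a no, not a missing value. The inpatient share would be tabulated but not joined to this variable. The yes/no form is fixed in Table 3, and section 9.8 says the protocol will be strictly followed. The absence of formal comparisons lessens the between-cohort issue but leaves the bias within each cohort.

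**Conclusion.** The point holds in a limited form. As written, an inpatient dose whose premedication is not captured counts as no use, although the protocol gives the adjacent variable a level for this situation. Supportive-medication use is therefore likely understated at the index date and, among patients with no captured claim in the window, in step-up. Over step-up the shortfall is generally smaller and is not proportional to inpatient starts.

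The direction rests on inpatient capture being incomplete, which the vial-size row and the premedication code list make likely but do not prove. The size is unknown. The range of 27% to 76.5% against an assumed 90% is illustrative, since no inpatient share, true use or capture rate is given. A reader might take the low end as an estimate, or conclude that inpatient premedication is never visible; the documents support neither. Nor does 9.9 confine its limitation to over-the-counter drugs. Its wording is wider, but inpatient drug capture is not named.

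**What to change.** For the index-date and step-up rows of the supportive-medication variable in Table 3:

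- Keep every observed yes, whatever the setting.
- Classify a patient with an inpatient index-drug dose in the window and no captured supportive-drug claim as unknown, inpatient, in parallel with the vial-size row.
- Report use by the care setting already collected, with the inpatient share alongside. For step-up, separate patients with only non-inpatient doses from those with any inpatient dose.
- Add a sentence to 9.9 naming incomplete capture of drugs given during inpatient stays.

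The unknown level should stay visible in the denominator. Dropping it would overstate use, because inpatient yes values are kept while inpatient no values are not. With *u* = 90%, *s* = 50% and *k* = 50%, the index date has 67.5% yes, 0.5 × 0.1 = 5% no and 27.5% unknown, and 67.5/72.5 = 93.1%. The non-inpatient stratum gives 45/50 = 90%. Restricting the analysis to patients with no inpatient dose at all is less attractive, since it discards observed yes values and selects on setting.

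The cost is one additional level, one table restructured and one limitation sentence. Strata become smaller: of 133 patients, an inpatient share of 30, 50 or 70% would leave about 93, 66 or 40 non-inpatient (133 × 0.7, 0.5, 0.3). Cells of 1 to 10 may be suppressed under the CMS policy in section 9.4.

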8. RESEARCH QUESTION AND OBJECTIVES

The overall aim of the study is to understand the real-world usage of elranatamab for the treatment of MM. To meet these objectives, the Clarify team will partner with Pfizer to create a curated dataset of Medicare FFS beneficiaries and their treatments to serve as the foundation upon which to examine descriptive data.

Specifically, the analysis will focus on the following primary research objectives:

Primary

- **Objective 1:** To describe the demographics, clinical history, and treatment history of patients treated with elranatamab
- Objective 2: To describe the administration and treatment management of elranatamab
 - Assess administration and management details (place of service, dosage, timing, frequency, supportive MM medication usage)
 - Evaluate dose, duration, and reasons for administration interruption or discontinuation, as available
- **Objective 3:** To describe all-cause and MM-related healthcare resource utilization (HCRU) and associated costs among patients treated with elranatamab

Exploratory

- Exploratory Objective 1: To describe the tolerability and real-world safety of elranatamab
- Exploratory Objective 2: To describe the overall effectiveness of elranatamab in terms of
- time to next treatment or death (TTNT/D) and overall survival (OS)
- Exploratory Objective 3: In a separate cohort, replicate all objectives for patients who initiated teclistamab

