9.7.2. Treatment Exposure Outcomes

Treatment exposure outcomes include RAI and time between administrations. The assessment periods shown in Table 4 are based on the elranatamab label instructions and will be used to measure treatment and dosing-related outcomes for patients receiving elranatamab.¹⁹ The assessment periods shown in Table 5 are based on the teclistamab label instructions and will be used to measure treatment and dosing-related outcomes for patients receiving teclistamab.²⁰ These periods are also provided in Figure 2.

Table 4. Dosing Schedule and Expected Administrations and Vial Size of Elranatamab

Dosing Schedule	Dosing Schedule Time Period		Vial Size
Step-Up	Index date - Day 8	3	44mg/1.1mL, 76mg/1.9mL
Maintenance Period 1	Day 9 - Day 168	1 per week	76mg/1.9mL

[figure not shown]
Maintenance Period 2	Day 169 - Censor	1 every two weeks	76mg/1.9mL
----------------------	------------------	-------------------	------------

Table 5. Dosing Schedule and Expected Administrations and Vial Size of Teclistamab

[figure not shown]
Dosing Schedule	Time Period	Expected Administrations	Vial Size
Step-Up	Index date - Day 7	3	30 mg/3mL
Maintenance Period	Day 8 - Censor	1 per week	153 mg/1.7mL

Figure 2. Dosing Schedule for Elranatamab and Teclistamab

Elranatamab label instructions

Teclistamab label instructions

Dosing outcomes (reported vial size, average time between claims, and frequency of claims) will be assessed during the above time periods regardless of whether the number of administrations during the period matches the number indicated on the label instructions.

Patients will be censored at the earliest of death, next treatment (CAR-T, BsAbs, bendamustine or belantamab), the end of part A or B continuous closed-claim coverage, or the end of data.

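### Primary Objective 2 promises dosage, but the only dose-like outcome is the reported vial size, which records the container and not the amount given

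*Protocol*

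**What the plan says.** Objective 2 is a primary objective. Section 8 breaks it into two tasks: "Assess administration and management details (place of service, dosage, timing, frequency, supportive MM medication usage") and "Evaluate dose, duration, and reasons for administration interruption or discontinuation, as available". The closing qualifier is attached to the second task only; dosage in the first has none.

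Section 9.3 presents its outcome table as complete: "Table 3 includes definitions and assessment periods for all study variables being used as outcomes". The one row there that resembles a dose opens "Reported vial size in the following categories (categorical"). Its elranatamab levels are two vial sizes, 44mg/1.1mL and 76mg/1.9mL, an inpatient dose whose vial is unknown, and a missing or unknown dose. For teclistamab the levels after the inpatient-unknown one are "30mg/3mL • 153mg/7mL • Missing dose/unknown dose".

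The analysis text in Section 9.7.2 follows the table: "Dosing outcomes (reported vial size, average time between claims, and frequency of claims) will be assessed during the above time periods". Table 4 in that section gives the elranatamab step-up line as "Index date - Day 8 3 44mg/1.1mL, 76mg/1.9mL", that is, three expected administrations and two vial sizes. Table 5 gives teclistamab three expected step-up administrations and one vial size, 30 mg/3mL.

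**The concern.** The objective asks how much drug patients received, and the variable answers which container was reported. The two agree only if each container corresponds to one amount. A schedule called step-up, with more administrations than vial sizes, suggests that it does not.

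The labels of Table 3's unknown levels use the word dose, so the table itself lets vial stand for dose. Section 9.9 discusses missing laboratory values, event severity, oncology endpoints and reasons for discontinuation, but does not say that the amount given is unrecoverable. A reader of the report could take a vial-size table as the dosage result of a primary objective.

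**Working it through.** The plan states no figure on this point, so there is nothing to reproduce. The check is a reading of the variables and a count.

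**1. Does any Objective 2 outcome measure an amount?** The Objective 2 rows of Table 3 are:
- supportive medication use (yes or no);
- reported vial size (categories);
- average time between claims (days);
- frequency of claims, split by vial size (count);
- Relative Administration Intensity (administrations received ÷ administrations expected, a ratio of counts; also Section 9.7.4);
- time to discontinuation (months);
- reason for discontinuation (category).

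None is in mg or billed quantity. Relative Dose Intensity is in the list of abbreviations, but no variable or analysis uses it.

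**2. How far can vial size separate the step-up doses?** Inputs are from Tables 4 and 5. With *n* administrations and *k* listed vial sizes, at least ⌈n/k⌉ administrations share a size.

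| Drug | n | k | At least this many share a size |
|---|---|---|---|
| Elranatamab | 3 | 2 | ⌈3/2⌉ = 2 |
| Teclistamab | 3 | 1 | ⌈3/1⌉ = 3 |

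For elranatamab, vial size can single out at most one of the three administrations. For teclistamab it singles out none, provided use follows Table 5. An administration in the inpatient-unknown or missing level is set apart only because its vial is not known, which says nothing about its amount.

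**3. Does vial size separate step-up from maintenance?** For elranatamab, the 76mg/1.9mL vial is listed in the step-up line and in both maintenance lines of Table 4. That vial alone does not tell the phases apart.

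**4. What does the plan still show?**
- A 44 mg vial in an elranatamab maintenance period would appear as a departure from Table 4.
- An extra step-up administration would appear in the claim count and in Relative Administration Intensity: four received against three expected gives 4/3 = 1.33.
- The order of claim dates ranks the administrations, without giving their amounts.

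What is lost is a change in amount while the vial size and the number of administrations stay the same.

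**5. Consistency of the variable.** The larger teclistamab vial is 153mg/7mL in Table 3 and 153 mg/1.7mL in Table 5. The two entries must be reconciled before the category can be coded.

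**The case against.** Four points can be made for the plan.

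- **The row is named honestly.** It is called reported vial size, it has levels for what is not known, and the second task under Objective 2 carries its own qualifier. This stands, but the first task lists dosage without one.

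- **The consequences are easy to overstate.** A reader might infer that the teclistamab step-up vial table must be a constant. It need not be. Table 5 gives the expected vial, while Table 3 records the reported one, in four levels, during the step-up period. An inpatient claim, a missing vial or the larger vial would all show. A reader might also infer that no dose reduction or repeated step-up dose could be detected. That goes too far as well, because changes of vial and of count remain visible. These points stand and limit the concern to changes within one vial size. The documents do not indicate how common such changes are.

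- **Some premises lie outside the Protocol.** The step-up amounts in mg are not in the readable text and Figure 2 is not shown, so the use of part-filled vials cannot be demonstrated. Annex 2 lists codes without descriptors. The Protocol does not describe billed units, a mg-per-unit conversion or discarded-drug lines. This also stands: the argument must rest on the counts in Tables 4 and 5, and the remedy must be conditional.

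- **The study is descriptive, and the SAP may modify the plan.** Both are true (Section 9.7) and both lower the stakes. They do not remove the mismatch: Table 3 claims to hold all outcome variables, and Section 9.8 commits the analysts to the algorithms described in the Protocol.

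**Conclusion.** The concern holds in a limited form. A primary objective names dosage, and no planned outcome measures an amount. In step-up, at least two of three elranatamab doses share a known vial size, as do all three teclistamab doses when use follows Table 5. A dose change within one vial size goes unseen; a change of vial or of the number of administrations does not. How often the unseen kind occurs cannot be estimated from the Protocol.

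The conclusion rests on the counts in Tables 4 and 5, on step-up meaning that the amount changes between administrations, and on Table 3 being complete as it states. No between-group comparison depends on it. This is a worthwhile, inexpensive improvement in how the objective is answered and reported, not a threat to the study.

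**What to change.** Add one row to Table 3: billed amount per administration (mg), derived as billed units × mg per unit on non-inpatient HCPCS lines that carry valid units. Separately billed discarded-drug lines would be left out. Report it by administration number and by dosing period, and keep reported vial size as a secondary description. Inpatient administrations stay unknown, and claims without valid units go to missing.

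Three things are assumptions to confirm in the data first: that units are available and valid, the mg-per-unit conversion, and how discarded drug is recorded.

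If the units prove unusable, reword Objective 2 as vial size and administration frequency. Also add a sentence to Section 9.9 saying that the amount given cannot be recovered from these claims. In either case, reconcile the larger teclistamab vial between Tables 3 and 5.

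If the fields are present, the cost is one derived variable and no new data collection. The drawbacks are some missing values, no gain for inpatient doses, and the fact that a billed amount is only a proxy for the dose given. The fallback costs two sentences.
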